Intraoperative characteristics will be presented as shown in mock [table 2](#).

Ventilatory variables

Ventilatory variables and other interventions will be reported hourly for 6 hours and in four specific periods: (1) 5 min after induction and beginning of ventilation (T_1); (2) 5 min after CO_2 insufflation (T_2); (3) 5 min after definitive positioning (immediately before beginning surgery) (T_3) and (4) 5 min after removal of pneumoperitoneum and return to supine (T_4). Peak, plateau and driving pressure (defined as plateau minus positive-end expiratory pressure (PEEP)) and PEEP levels, tidal volume size, respiratory rate, fraction of inspired oxygen (FiO_2), static and dynamic respiratory system compliance, pulse oximetry (SpO_2), heart rate, mean arterial pressure and pressure of CO_2 insufflation over the four specific periods will be analysed using a mixed model with repeated measures and plotted in an interaction plot (mock [table 3](#)).

Primary outcome

The number of patients developing a PPC will be reported in absolute numbers and percentages (mock [table 4](#)). The impact of ventilatory variables on the development of PPC will be assessed using a generalised linear mixed-effect model. Relevant covariates included in the final multivariable model will be identified as those with $p<0.2$ in the univariable model (including centre as a random effect), clinical relevance and no statistical association with other relevant variables. In the final model, time of measurement will be included as a fixed effect together with the variables of interest and the centres and patients will be included as random effect. The linearity of each continuous predictor with the log odds outcome will be checked graphically and, if not present, a log-transformation will be performed. Pearson correlation coefficients will be used to assess collinearity between predictors. Since a high collinearity between peak, plateau and driving pressure is expected, the main model will consider the variable with the higher amount of measurements between peak or plateau pressure. Driving pressure will be considered in a sensitivity analysis, excluding PEEP, peak and plateau pressure. Finally, the intraclass correlation coefficient (ICC) will be assessed. The ICC represents the ratio of between-site variance to total variance, ranging from 0 to 1.

Secondary outcomes

Secondary outcomes will be reported as shown in mock [table 4](#).

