Table 3 Intraoperative ventilation in four specific periods

| | Five minutes after induction and beginning of ventilation | | Five minutes after CO_2 insufflation | | Five minutes after definitive positioning | | Five minutes after desinsufflation and return to supine | |
|--|---|----------|---|----------|---|----------|---|----------|
| | Patients | P values | Patients | P values | Patients | P values | Patients | P values |
| Surgical positioning | | | | | | | | |
| Dorsal decubitus | n/Total (%) | | n/Total (%) | | n/Total (%) | | n/Total (%) | |
| Ventral decubitus | n/Total (%) | | n/Total (%) | | n/Total (%) | | n/Total (%) | |
| Lateral decubitus | n/Total (%) | | n/Total (%) | | n/Total (%) | | n/Total (%) | |
| Lithotomy | n/Total (%) | | n/Total (%) | | n/Total (%) | | n/Total (%) | |
| Trendelenburg | n/Total (%) | | n/Total (%) | | n/Total (%) | | n/Total (%) | |
| Reverse Trendelenburg | n/Total (%) | | n/Total (%) | | n/Total (%) | | n/Total (%) | |
| Sitting | n/Total (%) | | n/Total (%) | | n/Total (%) | | n/Total (%) | |
| Mode of ventilation | | | | | | | | |
| Pressure controlled | n/Total (%) | | n/Total (%) | | n/Total (%) | | n/Total (%) | |
| Volume controlled | n/Total (%) | | n/Total (%) | | n/Total (%) | | n/Total (%) | |
| PCVG | n/Total (%) | | n/Total (%) | | n/Total (%) | | n/Total (%) | |
| Other | n/Total (%) | | n/Total (%) | | n/Total (%) | | n/Total (%) | |
| Peak pressure, cmH_2O | Mean \pm SD | | Mean \pm SD | | Mean \pm SD | | Mean \pm SD | |
| Plateau pressure, cmH_2O | Mean \pm SD | | Mean \pm SD | | Mean \pm SD | | Mean \pm SD | |
| Driving pressure, cmH_2O | Mean \pm SD | | Mean \pm SD | | Mean \pm SD | | Mean \pm SD | |
| PEEP, cmH_2O | Mean \pm SD | | Mean \pm SD | | Mean \pm SD | | Mean \pm SD | |
| Tidal volume, mL/kg PBW | Mean \pm SD | | Mean \pm SD | | Mean \pm SD | | Mean \pm SD | |
| Respiratory rate, mpm | Mean \pm SD | | Mean \pm SD | | Mean \pm SD | | Mean \pm SD | |
| FiO_2 , % | Mean \pm SD | | Mean \pm SD | | Mean \pm SD | | Mean \pm SD | |
| Static C_{RS} , mL/ cmH_2O | Mean \pm SD | | Mean \pm SD | | Mean \pm SD | | Mean \pm SD | |
| Dynamic C_{RS} , mL/ cmH_2O | Mean \pm SD | | Mean \pm SD | | Mean \pm SD | | Mean \pm SD | |
| Use of recruitment manoeuvres | | | | | | | | |
| Increase in PEEP | n/Total (%) | | n/Total (%) | | n/Total (%) | | n/Total (%) | |
| Increase in tidal volume | n/Total (%) | | n/Total (%) | | n/Total (%) | | n/Total (%) | |

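### The main PPC model picks peak or plateau pressure by number of readings and prespecifies no ventilation-mode term, so if peak is picked and modes are mixed the pressure odds ratio can be biased

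*SAP*

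**What the plan says.** The Introduction gives the association between ventilatory parameters and outcomes as one of the study's aims. The relevant rules are in the Primary outcome section of the predefined statistical analysis plan:

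- **Choice of pressure.** "Since a high collinearity between peak, plateau and driving pressure is expected", only one pressure is kept, and "the main model will consider the variable with the higher amount of measurements between peak or plateau pressure". Collinearity is the only reason given.
- **Covariate screen.** Covariates qualify on a univariable p value below 0.2, together with "clinical relevance and no statistical association with other relevant variables". Mode is neither named nor excluded.
- **Terms of the final model.** Measurement time and the exposures under study are fixed; centre and patient are random. No mode term, pressure-by-mode term or mode-specific estimate is listed.
- **Sensitivity analysis.** "Driving pressure will be considered in a sensitivity analysis, excluding PEEP, peak and plateau pressure". The Ventilatory variables section defines driving pressure as plateau minus PEEP.

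Mock Table 3 has a block headed "Mode of ventilation" at each of the four periods, with rows for pressure controlled, volume controlled, PCVG and other.

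**The concern.** The rule treats peak and plateau pressure as substitutes and lets data completeness decide between them. They are not the same quantity, and the difference between them depends on mode. As general respiratory physiology (the SAP does not discuss it), peak under volume control is plateau plus the pressure needed to drive flow through the tube and airways. Under pressure control or PCVG it lies close to plateau. Peak is usually displayed in every mode, whereas plateau usually needs a pause, so a count of readings may well favour peak.

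In a cohort with mixed modes, a pooled peak coefficient then compares distending pressure in some patients with distending pressure plus resistance in others. Part of the spread in the exposure is simply mode. At stake is the main estimate for the ventilation-outcome aim, and it could mislead in size even with complete data.

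**Working it through.** **Inputs from the SAP.** The selection rule, the screen, the list of final-model terms and the recording of mode. The SAP gives no reading counts, mode shares, pressure SDs, target odds ratio or sample size, so there is no figure of its own to reproduce.

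**Assumptions, for illustration.** Plateau SD 5 cmH2O (variance 25). Peak equals plateau under pressure control or PCVG, and equals plateau plus a gap of mean d and SD 1.5 under volume control. The volume-control share is f. Mode is unrelated to both plateau and PPC. Plateau carries the effect of interest.

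**Step 1: pooled peak, no mode term.** The gap adds variance V = f × 1.5² + f(1 − f) × d². The share of the true log odds ratio retained is approximately 25/(25 + V).

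| f | d (cmH2O) | V | Retained | Loss |
|---|---|---|---|---|
| 10% | 4 | 0.225 + 1.44 = 1.665 | 25/26.665 = 0.94 | 6% |
| 10% | 8 | 0.225 + 5.76 = 5.985 | 25/30.985 = 0.81 | 19% |
| 20% | 4 | 0.45 + 2.56 = 3.01 | 25/28.01 = 0.89 | 11% |
| 20% | 8 | 0.45 + 10.24 = 10.69 | 25/35.69 = 0.70 | 30% |
| 50% | 4 | 1.125 + 4 = 5.125 | 25/30.125 = 0.83 | 17% |
| 50% | 6 | 1.125 + 9 = 10.125 | 25/35.125 = 0.71 | 29% |
| 50% | 8 | 1.125 + 16 = 17.125 | 25/42.125 = 0.59 | 41% |

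At an even split, a true log odds of 0.08 per cmH2O would be estimated as 0.066, 0.057 or 0.047 for gaps of 4, 6 or 8.

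**Step 2: mode term added.** The between-mode part drops out and the retained share becomes 25/(25 + f × 1.5²). That is 25/25.225 = 0.99 at f = 10% and 25/26.125 = 0.96 at f = 50%. What remains is the spread of the gap within volume control, which a mode term cannot remove.

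**Step 3: simulation with wider assumptions.** Single-level logistic models with 400,000 records per setting, true odds ratio 1.05 per cmH2O, f of 30%, 50% or 70%, and gaps of 3, 5 or 8 (SD 1.5, 2 or 3).

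- Mode unrelated to PPC: peak alone retained 0.54 to 0.93 of the log odds ratio (odds ratio 1.027 to 1.046). Peak plus mode retained 0.79 to 0.99 (1.040 to 1.049).
- Mode related to PPC (f = 50%, gap 5, SD 2), with log-odds effects of volume control of −0.5, −0.25, +0.25 and +0.5: peak alone gave 0.37, 0.57, 0.92 and 1.12 of the true value. The last is an odds ratio of 1.056, which is inflated. Peak plus mode gave 0.91 to 0.94 throughout.

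The simulation ignores repeated measures and random effects, so it shows direction and rough size only.

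**Step 4: would the screen bring mode in?** Under the Step 1 assumptions a single overall univariable test of mode is a test of a true null. It falls below 0.2 about 20% of the time, so mode would be dropped on that criterion about 1 − 0.2 = 80% of the time. If mode is related to PPC it may pass that criterion, yet it can still fail the no-association condition because it is related to peak pressure. In neither case does the screen reliably retain mode.

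**The case against.** A reader might infer that the SAP pools modes and leaves mode out. It does not say so. Mode is open to selection, and clinical relevance is one of the criteria. The accurate statement is that no mode term is prespecified.

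A reader might also infer that the odds ratio will be weakened. That needs mode to be unrelated to PPC. Step 3 shows the estimate can also be nearly unbiased or inflated.

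The problem is conditional as well. It arises only if peak has more readings than plateau and if the abdominal cohort mixes modes. Mode rows in an empty mock table show that mode is recorded, not that the mix is substantial. An even split is close to the worst case for a given gap; at 10% volume control and a gap of 4 the loss is only 6%. The word bias presumes that distending pressure is the target, which the SAP does not state. All of this stands and limits the point.

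The driving-pressure analysis is real but partial cover. Being built from plateau, it lacks readings in exactly the situation where peak is chosen, and it is not the main model.

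Finally, one might extend the criticism to the repeated-measures models of peak pressure and of "static and dynamic respiratory system compliance". That does not hold as a defect. Those models describe practice, mode changes between periods are part of that practice, and Table 3 shows mode, peak and plateau side by side.

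**Conclusion.** The point holds as a conditional weakness. The exposure in the main PPC model is chosen by data completeness alone, and the only route for mode into the model can shut it out because of its link with peak pressure. If peak is chosen and modes are mixed, the pooled odds ratio is a biased measure of distending pressure. The loss is about 6% to 41% of the log odds ratio for volume-control shares of 10% to 50% and gaps of 4 to 8 cmH2O, given plateau SD 5, gap SD 1.5 and mode unrelated to PPC. If mode is related to PPC, the direction is not fixed. None of these inputs is in the SAP, and the figures are not estimates for the planned multilevel model.

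The primary outcome itself, PPC incidence reported as counts and percentages, is unaffected. This is a cheap improvement to one association analysis.

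**What to change.** Add to the Primary outcome section: whenever peak pressure is the exposure in the PPC model, ventilation mode at each reading (volume controlled; pressure controlled or PCVG; other) enters as a fixed term, exempt from both the p<0.2 criterion and the no-association condition. Add two sensitivity analyses: a peak-by-mode check, and a version of the model using plateau pressure where it was measured.

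Mode is already collected at the four periods, so the cost is a sentence or two and a few degrees of freedom. The mode term reduces the bias but does not fully remove it (0.79 to 0.99 of the log odds ratio retained in the settings simulated with mode unrelated to PPC), which is why the plateau-based version is worth having despite fewer readings. A mode-adjusted version of the repeated-measures models of peak pressure and dynamic compliance is optional.

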| Red blood cells | n/Total (%) |
| Fresh frozen plasma | n/Total (%) |
| Platelets | n/Total (%) |
| Cryoprecipitate | n/Total (%) |
| Duration of surgery, min | Mean±SD |
| Duration of anaesthesia, min | Mean±SD |

controlled environment to maintain confidentiality. Electronic documents are controlled with password protection according to best practices.

Data management

The goal of the clinical data management plan is to provide high-quality data by adopting standardised procedures to minimise the number of errors and missing data, and consequently, to generate an accurate database for analysis. Remote monitoring is performed to signal early aberrant patterns, issues with consistency, credibility and other anomalies, according to predefined queries created in the system. Any missing and outlier data values are individually revised and completed or corrected whenever possible.

Cleaning and locking of the database

The database will be locked as soon as all data are entered and all discrepant or missing data are resolved—or if all efforts are employed and we consider that the remaining issues cannot be fixed. At this step, the data will be reviewed before database locking. After that, the study database will be locked and exported for statistical analysis. At this stage, permission for access to the database will be removed for all investigators and the database will be archived.

Sample size

All patients submitted to ventilation during general anaesthesia for RAS will be consecutively included during the period of 1 month, in a convenience sample.

Predefined statistical analysis plan

For the primary analyses, only patients undergoing abdominal surgery will be included. Also, patients in whom the surgery was converted to open or laparoscopic will be excluded. This group of patients excluded due to these reasons will be studied in a separate report. Continuous distribution of the data will be assessed by visual inspection of histograms and D'Agostino-Pearson's normality tests. Baseline characteristics will be expressed as counts and percentages, means and SD or medians and IQR whenever appropriate. Hypothesis tests will be two-sided with a significance level of 5%. We will not adjust p values for multiple comparisons. Analyses will

be performed using the R (R Core Team, 2016, Vienna, Austria) programme.

Baseline characteristics

Patients baseline characteristics will be presented as shown in mock [table 1](#).

Intraoperative characteristics

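### The driving-pressure sensitivity model leaves out PEEP for no stated reason, so its coefficient is not PEEP-adjusted and a difference from the main model can be ambiguous

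*SAP*

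**What the plan says.** All of this is in the predefined statistical analysis plan. The part on ventilatory variables gives the definition "driving pressure (defined as plateau minus positive-end expiratory pressure (PEEP", that is, plateau minus PEEP.

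The part on the primary outcome sets the model: "The impact of ventilatory variables on the development of PPC will be assessed using a generalised linear mixed-effect model". On the pressures it reasons "Since a high collinearity between peak, plateau and driving pressure is expected", and so "the main model will consider the variable with the higher amount of measurements between peak or plateau pressure". It then adds "Driving pressure will be considered in a sensitivity analysis, excluding PEEP, peak and plateau pressure".

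Three things are not written. No reason is given for leaving out PEEP. No model with both driving pressure and PEEP is planned. PEEP is never said to be in the main model; this is only implied by its being listed as excluded from the sensitivity model.

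**The concern.** The stated problem is overlap among three pressures, and PEEP is not one of them. Removing peak and plateau deals with that overlap. Removing PEEP as well does something else: it takes away adjustment for a ventilator setting that may be related both to driving pressure and to PPC, and that the plan tabulates in all four periods.

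At stake is the reading of the sensitivity analysis. If its driving-pressure result differs from the pressure result of the main model, the reader should know what changed. As planned, the pressure variable and the PEEP adjustment may both change, and the set of records may change with them.

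**Working it through.** The SAP gives no figure on this point, so there is none to reproduce. The definition of driving pressure (DP) is the SAP's. All SDs, effects and correlations below are assumptions.

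**1. Is PEEP redundant beside DP?** The set {plateau, DP, PEEP} has rank 2, because DP = plateau - PEEP. The set {DP, PEEP} also has rank 2. With plateau out, both can be estimated.

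**2. What does dropping PEEP impose?** With linear terms,

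b1 × plateau + b2 × PEEP = b1 × DP + (b1 + b2) × PEEP.

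Write g = b1 + b2, the PEEP effect at fixed DP. The DP-only model is the special case g = 0, that is b2 = -b1.

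**3. How far does the DP coefficient move?** Approximately

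shift = g × r × SD(PEEP) / SD(DP),

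where r is the correlation of DP with PEEP. The shift is zero if r = 0 or g = 0.

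**4. Check by simulation.** Logistic regression, n = 400,000, no random effects. Assumed: SD(DP) 5, SD(PEEP) 2, DP log-odds 0.05 per cmH2O, so the true odds ratio per 5 cmH2O is exp(0.25) = 1.284.

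| r | g | OR per 5 cmH2O, PEEP kept | PEEP dropped | Formula, PEEP dropped |
|---|---|---|---|---|
| -0.5 | -0.10 | 1.285 | 1.415 | exp(5 × 0.070) = 1.419 |
| -0.5 | 0 | 1.286 | 1.286 | exp(5 × 0.050) = 1.284 |
| -0.5 | +0.10 | 1.292 | 1.168 | exp(5 × 0.030) = 1.162 |
| -0.3 | -0.10 | 1.297 | 1.378 | exp(5 × 0.062) = 1.363 |
| 0 | -0.10 | 1.282 | 1.280 | exp(5 × 0.050) = 1.284 |
| +0.3 | -0.10 | 1.267 | 1.194 | exp(5 × 0.038) = 1.209 |
| +0.3 | +0.10 | 1.286 | 1.367 | exp(5 × 0.062) = 1.363 |

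The formula agrees with the simulation to within 0.02. The direction depends on the signs of r and g.

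**5. A second set of assumed inputs.** SD(DP) 4.5, SD(PEEP) 2.5, PEEP odds ratio 0.90 per cmH2O at fixed DP, so g = ln 0.90 = -0.105.

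- r = -0.3: shift = 0.105 × 0.3 × 2.5/4.5 = 0.0176, a factor of exp(5 × 0.0176) = 1.09 per 5 cmH2O.
- r = -0.5: shift = 0.0293, a factor of 1.16.
- r = +0.3: shift = -0.0176, a factor of 0.92.

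With no true DP effect, these factors are the apparent odds ratios. With a true odds ratio of 1.05 per cmH2O (1.05^5 = 1.28 per 5 cmH2O), the apparent values are about 1.39, 1.48 and 1.17.

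**6. What does a DP + PEEP model add?** That depends on the main-model variable.

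- *Plateau.* By step 2, DP + PEEP on the same records is plateau + PEEP rewritten. In all 12 simulated scenarios the DP coefficient equalled the plateau coefficient (for example 0.0502 and 0.0502) and the log-likelihoods were the same. The new information is a direct estimate of g, and a test of g = 0 against the DP-only fit.
- *Peak.* DP + PEEP is a different model. Peak is chosen because it has more measurements than plateau, and DP exists only where plateau was recorded, so the records will normally differ too.

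**The case against.** The strongest reply is that the planned model is deliberate. PEEP is a component of driving pressure, so replacing the components by the composite is a recognisable choice. If plateau is the main-model variable, the DP-only model is nested in the main model, and it is the version that tells the reader something new. Putting DP + PEEP in its place would give the main model twice. This stands, and it is why the planned model should be kept and supplemented.

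A second reply is that the covariate rule, which asks for "clinical relevance and no statistical association with other relevant variables", already counts against entering two correlated pressures. It does point that way, but it depends on the data. It does not explain excluding PEEP by name whatever the data show.

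Third, the sizes above rest on assumed values and on a simulation without the planned centre and patient effects or time term. That is correct. They show that a shift is possible and can go either way, not how large it will be here.

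A reader might also infer that the DP coefficient absorbs any PEEP effect, or that the two models cannot be compared. Neither is supported. Only the part carried by the correlation moves across. With plateau as the main-model variable and the same records, the two models differ by one testable restriction.

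**Conclusion.** The point holds as a minor one. The plan's only driving-pressure coefficient is not PEEP-adjusted, and the collinearity reason given does not call for that. Under the assumed inputs the distortion is a factor of roughly 0.92 to 1.16 per 5 cmH2O. It vanishes if driving pressure and PEEP are uncorrelated or if PEEP has no effect at fixed driving pressure. The document settles neither size nor direction.

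The ambiguity is greatest when peak is the main-model variable. The statement that PEEP adjustment changes between the models assumes that PEEP is in the main model, which the SAP only implies. The equivalence of DP + PEEP and plateau + PEEP assumes linear terms and identical records; the log-transformation the SAP allows for non-linear predictors would break it.

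This is a sensitivity analysis of an association model. It would be wrong to infer that the primary outcome, a count and percentage of patients with a PPC, is affected.

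**What to change.** Keep the driving-pressure-only model and add to the SAP's text on the primary outcome:

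*A further model will include driving pressure and PEEP and exclude peak and plateau pressure. The main model will be repeated on the records in which plateau pressure is available, so that all three fits use the same records. The coefficient of driving pressure without PEEP is not adjusted for PEEP. With linear terms, driving pressure plus PEEP is a reparametrisation of plateau plus PEEP; if plateau is the main-model variable, comparison with the driving-pressure-only fit tests whether PEEP has no effect at a given driving pressure.*

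The text should also say whether PEEP is in the main model and why it is left out of the planned sensitivity model. Report the PEEP coefficient with its confidence interval as well as the test: patients are "consecutively included during the period of 1 month, in a convenience sample", so the test may have little power and a non-significant result would not show that the restriction holds.

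The cost is a few sentences, one or two extra model runs on data already collected, and one more parameter in the added model.
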